| SOP | Standard Operating Procedure |
| SUSAR | Suspected Unexpected Serious Adverse Reaction |
| US | United States |
| WHO | World Health Organization |

PROTOCOL SUMMARY

Title: A Trial of the Safety and Immunogenicity of the COVID-19 Vaccine (mRNA-1273) in Participants with Hematologic Malignancies and Various Regimens of Immunosuppression, and in Participants with Solid Tumors on PD1/PDL1 Inhibitor Therapy, Including Booster Doses of Vaccine

Design of the Study: This is an open-label, multicenter clinical trial designed to evaluate the safety, reactogenicity and primary immunogenicity of the mRNA-1273 vaccine administered in 2 doses, 28 days apart, in participants who have hematological malignancy and are immunosuppressed due to their disease and/or treatment or receiving a PD-1/PDL-1 inhibitor for treatment of a solid tumor can be associated with appropriately high rates of development of neutralizing antibodies of mRNA-1273. The trial will also evaluate the safety, reactogenicity and immunogenicity after administration of additional “booster” doses of the vaccine.

Study Phase: 2

Study Population: For the vaccine-naïve cohorts, up to 80 participants will be enrolled.

- 20 participants with solid tumor malignancies who have initiated PD1/PDL1 inhibitor therapy as part of standard of care and are deemed to have a stable regimen without the need for any immunosuppressive therapy or corticosteroids.
- 60 participants with leukemia, lymphoma, multiple myeloma and participants post-allogeneic stem cell transplant will be enrolled based on their perceived risk of immunosuppression.

For the previously-vaccinated (also known as “booster”) cohorts, up to 140 participants will be enrolled for booster injections. All participants on the vaccine-naïve cohorts will have the option of receiving boosters; however, they will not count towards the maximum accrual goal for each of the booster groups. Note: All participants will be eligible to receive up to three (3) booster doses of vaccine on study.

- 20 participants with solid tumor malignancies who have initiated PD1/PDL1 inhibitor therapy as part of standard of care and are deemed to have a stable regimen without the need for any immunosuppressive therapy or corticosteroids.
- 20 participants with chronic lymphocytic leukemia who are not currently on any therapies
- 20 participants with chronic lymphocytic leukemia who are on BTK inhibitor therapy alone

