3 STUDY DESIGN, OBJECTIVES AND ENDPOINTS OR OUTCOME MEASURES

3.1 Study Design Description

This is an open-label, multicenter clinical trial designed to evaluate the safety, reactogenicity and primary immunogenicity of the novel LNP-encapsulated mRNA-based vaccine that encodes for a full-length, prefusion stabilized spike (S) protein of SARS-CoV-2 manufactured by ModernaTX, Inc. in a specific population of patients with either hematologic malignancies under active treatment or patients with solid tumors who are undergoing treatment with PD1/PDL1 inhibitors.

For the vaccine-naïve cohorts, the vaccine will be administered in 2 doses, 28 days apart. Up to 80 participants will be enrolled into one of four vaccine-naïve cohorts. Participants will receive an IM injection (0.5 mL) of mRNA-1273 on Day 1 and Day 29 in the deltoid muscle and will be followed through 12 months post second vaccination (Day 394).

For the booster-vaccine cohorts, the booster vaccine will be administered in a single dose. Up to 120 participants will be enrolled into one of 6 booster-vaccine cohorts. Participants will receive an IM injection (0.5 mL) of mRNA-1273 on Day 1 in the deltoid muscle and will be followed through 12 months post vaccination (Day 360). For participants who choose to receive an additional (second) booster dose of the vaccine, the second booster dose of mRNA-1273 must be administered at least 4 weeks after their previous dose of the vaccine. Similarly, for participants who choose to receive a third booster dose of the vaccine, the third booster dose of mRNA-1273 must be administered at least 4 weeks after their previous dose of the vaccine. Note: Participants may enroll on this study only to receive a second or a third booster dose and will be counted/analyzed in the identified booster-vaccine cohorts.

Participants initially enrolled in the vaccine naïve cohort will also have the option to receive the first booster dose no less than 4 weeks after their second dose; with the similar option for a second or third booster on the same schedule as the booster-vaccine cohorts. If they choose to receive this, they will adhere to the booster vaccine calendar and will be analyzed also as part of the booster vaccine group.

Safety data will be reviewed by the assigned Safety Monitoring Committee (SMC) as explained in section [8.10.1](#).

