3.2 Study Objectives and Endpoints

| Objectives and Endpoints | |
|--|--|
| Primary Objective | Primary Endpoints |
| Safety Objective: To evaluate the safety and reactogenicity of the mRNA-1273 vaccine administered in 2 doses 28 days apart, in participants who have a | Safety Endpoints: 
Solicited local and systemic Adverse Reactions (ARs) through 7 days after each injection. |

| Objectives and Endpoints | |
|--|---|
| Primary Objective | Primary Endpoints |
| hematological malignancy and are immunosuppressed due to their disease and/or treatment, or receiving a PD-1/PDL-1 inhibitor for treatment of a solid tumor for participants who are vaccine- naïve. To evaluate the safety and reactogenicity of booster doses of mRNA-1273 vaccine administered to participants with cancer who have previously received an mRNA or alternative vaccine regimen | 
Unsolicited AEs through 28 days after each injection.SAEs throughout the entire study period.Vital sign measurements and physical examination findings. |
| Immunogenicity Objective: To assess the immunogenicity of mRNA-1273 in participants with cancer, as assessed by the titer or level of specific binding antibody (bAb) | Immunogenicity Endpoints: 
Titer or level of specific binding antibody (bAb), in participantsTiter or level of SARS-CoV-2-specific binding antibody (bAb) measured by ELISA on Day 1, Day 29, Day 36, Day 57 Day 209 and Day 394 for participants on Vaccine-Naïve CohortsTiter or level of SARS-CoV-2-specific binding antibody (bAb) measured by ELISA on Day 1, Day 29, Day 180, Day 360 for participants on Booster Vaccine Cohorts |

| Secondary Objective | Secondary Endpoints |
|---|--|
| To evaluate the immunogenicity of the mRNA-1273 vaccine administered, as assessed by the titer or level of neutralizing antibody (nAb). | For Vaccine-Naïve Cohorts: 
Titer or level of SARS-CoV-2-specific neutralizing antibody (nAb) on Day 1, Day 29, Day 36, Day 57, Day 209, and Day 394Seroconversion due to vaccination on Day 29, Day 36, Day 57, Day 209, and Day 394 measured as:
For subjects with no detectable antibody titer (< |

| Secondary Objective | Secondary Endpoints |
|---------------------|---|

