11.4.1.2 Per-Protocol Set

The Per-Protocol (PP) Set consists of all FAS participants who meet all of the following criteria:

- Complied with the injection schedule.

- Complied with the timings of immunogenicity blood sampling to have post-injection results available for at least one assay component corresponding to the immunogenicity analysis objective.
- Have had no major protocol deviations that impact immune response during the period corresponding to the immunogenicity analysis objective.

The PP Set will serve as the primary set for the analysis of immunogenicity data in this study.

11.4.1.3 **Solicited Safety Set**

The Solicited Safety Set consists of all participants who received at least one study injection, and contribute any solicited AR data; i.e., have at least one post-baseline solicited safety assessment. The Solicited Safety Set will be used for the analyses of solicited ARs.

11.4.1.4 **Safety Set**

The Safety Set consists of all participants who received at least one study injection. The Safety Set will be used for analysis of safety except for the solicited ARs.

11.4.2 **Statistical Analyses**

11.4.2.1 **Immunogenicity Analyses**

The analyses of immunogenicity will be based on the PP Set. If the number of participants in the FAS and PP Set differ (defined as the difference divided by the total number of participants in the PP Set) by more than 10%, supportive analyses of immunogenicity may be conducted using the FAS.

For the primary immunogenicity endpoint, geometric mean titer (GMT) of specific bAb with corresponding 95% CI at each timepoint and geometric mean fold rise (GMFR) of specific bAb with corresponding 95% CI at each post-baseline timepoint over pre-injection baseline at Day 1 will be provided. Descriptive summary statistics including median, minimum, and maximum will also be provided.

For the secondary immunogenicity endpoint, GMT of specific nAb with corresponding 95% CI at each timepoint and GMFR of specific nAb with corresponding 95% CI at each post-baseline timepoint over pre-injection baseline at Day 1 will be provided. Descriptive summary statistics including median, minimum, and maximum will also be provided. For summarizations of GMT values, antibody values reported as below the LLOQ will be replaced by $0.5 \times \text{LLOQ}$. Values that are greater than the upper limit of quantification (ULOQ) will be converted to the ULOQ.

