11.4.2.2 Safety Analyses

Safety and reactogenicity will be assessed by clinical review of all relevant parameters including solicited ARs (local and systemic events), unsolicited AEs, SAEs, AEs leading to discontinuation, safety laboratory test results, vital signs, and physical examination findings.

Solicited ARs and unsolicited AEs will be coded by system organ class (SOC) and preferred term according to the MedDRA for adverse reaction terminology. The Toxicity Grading Scale for Healthy Adult and Adolescent Volunteers Enrolled in Preventative Vaccine Clinical Trials (DHHS 2007) is used in this study with modification for rash, solicited ARs, unsolicited AEs, and vital signs.

Rash will be graded as:

- Grade 0 = no rash
- Grade 1 = localized without associated symptoms
- Grade 2 = maculopapular rash covering $< 50\%$ body surface area
- Grade 3 = urticarial rash covering $> 50\%$ body surface area
- Grade 4 = generalized exfoliative, ulcerative or bullous dermatitis

All safety analyses will be based on the Safety Set, except summaries of solicited ARs which will be based on the Solicited Safety Set. All safety analyses will be provided overall and by cohort.

The number and percentage of participants with any solicited local AR, with any solicited systemic AR and with any solicited AR during the 7-day follow-up period after each injection will be provided with a 2-sided 95% exact CI using the Clopper-Pearson method.

Number and percentage of participants with unsolicited AEs, SAEs, Grade 3 or higher ARs and AEs, treatment-related AEs and SAEs, and AEs leading to discontinuation from study vaccine or participation in the study will be summarized. Unsolicited AEs will be summarized by system organ class and/or preferred term coded by MedDRA.

For treatment-emergent safety laboratory tests results, the raw values and change from baseline values will be summarized by timepoint.

The number and percentage of participants who have chemistry, hematology, coagulation, and vital signs results below or above the laboratory normal ranges will be tabulated by timepoint.

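### Unsolicited and Grade 3+ AE percentages pool people with different numbers of injections; a per-injection 28-day table is needed

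*Combined protocol and SAP*

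**What the plan says.** **Endpoint.** Section 3.2 lists "Unsolicited AEs through 28 days after each injection" as a primary safety endpoint, together with SAEs over the whole study.

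**Analysis.** Section 11.4.2.2 will summarise "Number and percentage of participants with unsolicited AEs, SAEs, Grade 3 or higher ARs and AEs, treatment-related AEs and SAEs", along with AEs leading to discontinuation. It adds: "All safety analyses will be provided overall and by cohort". No per-injection breakdown, common window or exposure-adjusted rate is stated for these events. Solicited reactions are handled differently: their percentages "during the 7-day follow-up period after each injection will be provided with a 2-sided 95% exact CI".

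**Denominator.** Section 11.4.1.4: "The Safety Set consists of all participants who received at least one study injection". The number of injections plays no part.

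**Doses.** Section 3.1: "For the vaccine-naïve cohorts, the vaccine will be administered in 2 doses, 28 days apart"; and "For the booster-vaccine cohorts, the booster vaccine will be administered in a single dose". The Protocol Summary notes: "All participants will be eligible to receive up to three (3) booster doses of vaccine on study". Section 3.1 also says that naïve participants who take a booster are analysed in the booster group as well. It does not say which group carries their events.

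**Collection.** Section 8.3, repeated in the calendar notes of Appendices F and G, collects all AEs continuously from Day 1 until 28 days past the final dose. After that, only SAEs judged related are recorded.

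**The concern.** The endpoint is defined by injection, but the summary is by participant. Someone with two injections has twice the 28-day window of someone with one, and both count once in the same denominator. A group given more injections can therefore show a higher percentage although the risk per injection is the same.

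This matters because these are primary safety endpoints in an uncontrolled study of patients who have many AEs from their disease and treatment. The protocol also has separate safety objectives for the two-dose series and for boosters. A single percentage for a naïve participant who goes on to boosters answers neither.

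**Working it through.** **1. The plan's own figure.** Naïve: 4 × 20 = 80. Booster: 20 + 20 + 30 + 20 + 20 + 20 + 10 = 140. Total 80 + 140 = 220, which agrees with Section 11.2. (Section 3.1 still gives 120 booster participants, hence 200. That does not bear on this point.) No AE rate, booster uptake or safety precision is stated anywhere.

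**2. Injections and windows.** Planned doses (Section 3.1; Tables 1 and 2 in Section 4.6) are 2 in cohorts 1-4 and 1 in cohorts 5-11. The individual maximum is 2 + 3 = 5 for a naïve participant and 3 for a booster-cohort participant. Under Section 3.2 at minimum spacing the window is 28 × doses: 28 days for one, 56 for two, 84 for three, 140 for five. By design that is 2:1 between arms. Under the continuous rule in Section 8.3 the gap can widen. With an assumed 90 days between extra doses, a booster participant has 28, 28 + 90 = 118 or 28 + 180 = 208 days for one, two or three doses.

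**3. Effect on the percentage.** Assume a constant probability p of at least one AE per 28 days. Over k windows the crude percentage is 1 − (1 − p)^k.

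| Assumed p | 1 dose | 2 doses | 3 doses |
|---|---|---|---|
| 5% | 5.0% | 9.8% | 14.3% |
| 10% | 10.0% | 19.0% | 27.1% |
| 20% | 20.0% | 36.0% | 48.8% |

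Risk per injection is identical along each row. If risk varies between patients, the growth is smaller. With mean 20% and an assumed Beta(0.4, 1.6) spread, two doses give 1 − (1.6/2)(2.6/3) = 31% instead of 36%.

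**4. The overall figure.** At p = 10% with planned doses only and full enrolment: (80 × 19% + 140 × 10%)/220 = 29.2/220 = 13.3%. This describes neither schedule and moves with the enrolment mix.

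**5. Within an arm.** Planned exposure is equal. Let each successive optional booster be taken with probability u. At p = 10% a booster cohort reads 10.0% at u = 0, 0.5 × 10 + 0.25 × 19 + 0.25 × 27.1 = 16.5% at u = 0.5, and 27.1% at u = 1. The size depends entirely on u, which the documents do not give.

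**6. SAEs.** If SAEs are collected throughout the study (Section 3.2), planned follow-up for unboosted participants ends at Day 394 or Day 360. A 10% risk over 360 days becomes 1 − 0.9^(393/360) = 10.9%, a small difference. If unrelated SAEs stop 28 days after the last dose (Section 8.3), the planned windows are 56 and 28 days.

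**7. Sampling error.** For true rates of 10% and 19% in two cohorts of 20, the standard error of the difference is √(0.1 × 0.9/20 + 0.19 × 0.81/20) = 11 points. The Clopper-Pearson 95% interval for 2/20 is 1.2% to 31.7%.

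**The case against.** The strongest reply is that the study is descriptive. Section 11.1 rules out hypothesis testing, no formal comparison of arms is planned, and with 10 to 30 people per cohort the intervals are wider than the shift at issue. Treatment-related events are tabulated separately, which limits background noise. Participants who miss the second dose stay for all safety assessments (Section 4.5), and those who withdraw are encouraged to allow AE follow-up (Section 6.1.4), which limits the effect of dropout.

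Much of this stands. It makes the point a gap in reporting and interpretation, not an invalid test. It does not remove it: without tests or a control group the percentages are themselves the safety result, wide intervals do not correct a systematic shift, and related events also accumulate with each injection.

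Three stronger readings are tempting and go too far.
- A reader might infer that cohort percentages mainly reflect time at risk. The documents do not show this. Planned exposure is equal among cohorts 1-4 and among cohorts 5-11, uptake and AE rates are unknown, and chance or real differences between diseases can be as large.
- A reader might infer that all-cause SAEs build up over repeated 12-month follow-ups because the calendar restarts at each booster (Section 6.1.3). Section 8.3 records later SAEs only if related, and the Protocol Summary gives about 14 months per participant.
- A reader might take five injections as typical of naïve cohorts. It is an individual maximum, and it inflates a naïve-cohort percentage only if all events after boosters are kept there. Section 3.1 leaves that open.

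**Conclusion.** The point holds as a limited one. The overall and naïve-versus-booster percentages for unsolicited and Grade 3+ AEs are confounded with number of injections and collection window, 2:1 by design. Under a constant-risk assumption the one-dose against two-dose reading is 5.0% v 9.8%, 10% v 19% or 20% v 36% at 5%, 10% or 20% per 28 days, and the gap is smaller if risk varies between patients. Those rates are assumptions. Within an arm, any distortion comes only from optional boosters, missed doses and dropout, and its size cannot be derived from the documents. For SAEs no magnitude can be fixed until the two collection rules agree.

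**What to change.** In Section 11.4.2.2:
- Tabulate unsolicited and Grade 3+ AEs by injection (Dose 1, Dose 2, booster 1, 2 and 3) within 28 days of that injection, truncated at the next injection so that no event is counted twice. Use recipients of that injection as the denominator.
- Count post-booster events of naïve participants under the booster injection.
- Keep the crude participant counts alongside. They also retain events collected outside any 28-day window.

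For SAEs, first reconcile Section 3.2 with Section 8.3 and the notes in Appendices F and G. Any person-time rate should then use only the time during which that class of SAE is collected. Dividing by time to last contact would include months in which unrelated SAEs may not be recorded.

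The cost is SAP wording and table shells. Dose dates (Section 4.5) and AE onset dates (Section 8.1.1) are already recorded. The downside is a few more tables, with small denominators for the later boosters.

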5.1 Inclusion Criteria

Participants must meet all the inclusion criteria in order to be eligible to participate in the study.

5.1.1 Participants must have one of the following:

- Histologically or cytologically confirmed solid tumor receiving a standard of care PD1/PDL1 inhibitor for treatment of their solid tumor (inclusive of Hodgkin Lymphoma and Primary Mediastinal B-Cell Lymphoma participants receiving PD1/PDL1 inhibitors as standard of care therapy)
- Confirmed diagnosis of acute leukemia (myeloid (AML) or lymphoid (ALL) or other acute leukemia; multiple myeloma; Waldenstrom macroglobulinemia

- Confirmed diagnosis of lymphoma, including small lymphoblastic lymphoma (i.e., chronic lymphocytic leukemia)
- Be post allogeneic stem cell transplantation (for any indication)
- Be an adult patient (aged 18 or older) with any malignancy who does not fit any of the above categories

5.1.2 Age \geq 18 years.

5.1.3 History of adequate organ and marrow function on a recent laboratory assessment (within 4 weeks of administration of vaccine), as defined below:

| | |
|---|---|
| Absolute lymphocyte count | Minimum value of 200 cells per mcL |
| Absolute neutrophil count | Minimum value of 500 cells per mcL |
| Platelets | Minimum value of 25,000 cells per mcL |
| Total bilirubin | Maximum value of 3.0 x upper limit of normal |
| AST(SGOT)/ALT(SGPT) | Maximum value of 5.0 x upper limit of normal |
| Creatinine | Maximum value of 3.0 x upper limit of normal (if elevated, use of creatinine calculated clearance will be necessary, as below) |
| Creatinine clearance (only necessary for participants with elevated creatinine) | For participants with Chronic Kidney Disease, a calculated Glomerular Filtration Rate minimum will be required as follows: $>30 \text{ mL/min}/1.73 \text{ m}^2$ for participants with creatinine levels above institutional normal. |

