7.2.2.2 Concomitant Medications

Recommendations with regard to specific types of concomitant therapies, supportive care; diet and other interventions are as follows:

- Concomitant medications are recommended as prophylaxis for nausea, vomiting, and infections, and are recommended according to institutional standards. Myelosuppression is expected in participants with acute leukemia, lymphoma or myeloma, or post-stem cell transplantation due to underlying disease, as well as due to chemotherapy, or both. Many participants may have neutropenia, thrombocytopenia, or both at study entry.
- Significant or life-threatening myelosuppression may be managed with growth factor support and blood transfusion according to institutional standard of care, American Society of Clinical Oncology (ASCO) Practice Guidelines, and/or NCCN Practice Guidelines.
- Infections secondary to myelosuppression are common in participants with hematologic malignancies, and may be related to underlying disease, chemotherapy, or both. Therefore, the use of prophylactic antibiotics, antifungal agents, and antiviral agents is recommended according to institutional standards.
- If a prohibited medication is considered essential for the participant well-being, continuation on study with concomitant administration of such medication(s) will need to be discussed with and approved by the principal investigator.

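### Laboratory out-of-range counts are not tied to each participant's own baseline, so in a population admitted with marked abnormalities they cannot show who newly worsened

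*Combined protocol and SAP*

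**What the plan says.** Section 11.4.2.2 plans two summaries of laboratory data.

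- For safety laboratory tests, "the raw values and change from baseline values will be summarized by timepoint".
- For chemistry and hematology, a number and percentage of participants, in a table where "coagulation, and vital signs results below or above the laboratory normal ranges will be tabulated by timepoint".

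The second summary has no grade, no rule for new or worsened results and no cross-tabulation against baseline. No change-from-baseline summary is stated for vital signs, although Section 3.2 lists them among the primary safety endpoints.

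Section 5.1.3 sets these entry limits:

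- Lymphocytes: "Minimum value of 200 cells per mcL"
- Neutrophils: "Minimum value of 500 cells per mcL"
- Platelets: "Minimum value of 25,000 cells per mcL"
- AST/ALT: "Maximum value of 5.0 x upper limit of normal"
- Bilirubin and creatinine, each: "Maximum value of 3.0 x upper limit of normal"

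Section 7.2.2.2, written for the hematologic cohorts, adds: "Many participants may have neutropenia, thrombocytopenia, or both at study entry".

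**The concern.** A count of out-of-range results is informative when nearly everyone starts in range. Here the entry criteria admit people well outside it. Assume a lower limit of normal for platelets of 150,000 per mcL, which the documents do not state. A participant stable at 60,000 is then low at every visit. A participant who falls from 140,000 to 30,000 is also low at every visit, and the table treats the two alike.

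The trial has no control arm, so each participant's pre-dose value is the only reference within the trial. Safety is a primary objective and Section 8.1.5 names thrombocytopenia as an event of special interest. A table that cannot separate entry state from change after vaccination gives little help with that objective in the cohorts where cytopenia is common.

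**Working it through.** The plan states no abnormality rate, test or power for this analysis, so there is no figure to reproduce. Two checks apply.

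**1. What by-timepoint counts can identify.** Take a cohort of 20, the usual size in Section 4.6, with illustrative counts of 10 low at Day 1 and 12 low at Day 29. Let n be the number newly low and r the number recovered.

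- 10 − r + n = 12, so n = 2 + r.
- Only 20 − 10 = 10 participants started in range, so n ≤ 10 and r ≤ 8.
- New onset therefore lies anywhere from 2 to 10. The counts fix only the net rise of 2.

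Worsening among the 10 already low does not enter the counts at all. A mean or median change does not fill the gap, because opposite individual changes can cancel.

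**2. How much of the post-dose count was present at entry.** Let b be the proportion out of range at baseline, s the probability that this persists, and q the probability of new onset among those in range. All three are assumptions.

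Share already abnormal = b·s / [b·s + (1 − b)·q]

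For example, with b = 0.05, s = 0.8 and q = 0.10, the share is 0.040 / (0.040 + 0.095) = 30%. With s from 0.8 to 0.9:

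| b | q = 0.02 | q = 0.05 | q = 0.10 | q = 0.20 |
|---|---|---|---|---|
| 0.05 | 68–70% | 46–49% | 30–32% | 17–19% |
| 0.10 | 82–83% | 64–67% | 47–50% | 31–33% |
| 0.30 | 94–95% | 87–89% | 77–79% | 63–66% |
| 0.50 | 98% | 94–95% | 89–90% | 80–82% |

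The share passes one half when b > q/(q + s). That is about 2% at q = 0.02, 5–6% at q = 0.05, 10–11% at q = 0.10 and 18–20% at q = 0.20.

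**Vital signs, side by side.** The wide-entry argument does not carry over: Sections 5.2.2 and 5.2.14 exclude febrile participants and uncontrolled hypertension. The problem is the reference, because vital signs have no laboratory normal range. Appendix D does grade them, but Grade 1 starts at 17 breaths per minute and 141 mm Hg systolic. Under assumed normal distributions with no vaccine effect and a half-unit correction:

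- Respiratory rate, mean 16, SD 2 to 2.5: P(Z > 0.5/2) = 40% to P(Z > 0.5/2.5) = 42% are Grade 1 or higher.
- Systolic pressure, mean 125, SD 14: P(Z > 15.5/14) = 13%. Mean 130, SD 15: P(Z > 10.5/15) = 24%.

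One-grade shifts on this scale will therefore often be ordinary variation.

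**Coagulation.** It is tabulated in Section 11.4.2.2 but is absent from the safety laboratory list in Section 7.3.1.

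**The case against.** The strongest reply has four parts.

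- **Change from baseline is already planned for laboratory tests.** This is correct, and a reader who inferred from the quoted sentence that the plan ignores baseline would be wrong. The gap is confined to the participant-level counts and to vital signs.
- **Day 1 would appear in a by-timepoint table.** If it is tabulated, toxicity that pushes participants across a limit raises later counts above it. It would therefore be too strong to say the tables would look the same after an inert injection. The net rise is visible; offsetting shifts and worsening among those already abnormal are not.
- **Adverse event reporting is a second route.** Thrombocytopenia is reported on the SAE timeline (Section 8.1.5), worsening of a pre-existing condition is an adverse event (Section 8.1.1), and unsolicited events are graded by CTCAE v5. New toxicity is therefore not simply hidden. But the route is partial. Section 8.4 records a laboratory abnormality only if it cannot be attributed to chemotherapy and meets listed conditions. Appendix C restricts hematologic event recording in acute leukemia and CLL, although its item f lets protocol text prevail.
- **The study is descriptive.** Section 11.1 rules out hypothesis testing, so no primary test is invalidated. That limits the weight of the point but does not remove it.

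**Conclusion.** The point holds for the laboratory counts. They mix pre-existing with new or worsened abnormality, the planned group-level change does not separate the two for individuals, and the adverse event route covers only part of the gap. The size of the ambiguity is shown by the 2-to-10 range in a cohort of 20.

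A reader might go further and infer that most counted abnormalities precede the vaccine. The documents do not support that in general. They give no proportion abnormal at entry, and the expectation of cytopenia concerns the hematologic cohorts, while up to 20 + 20 + 10 = 50 of 220 places are in solid-tumor cohorts 4, 8 and 11. A majority is plausible for blood counts in the hematologic cohorts, since the break-even prevalence is only about 2–20% for new-onset rates of 2–20%. It fails where entry abnormality is uncommon (30–32% at b = 0.05, q = 0.10), and it is not shown for vital signs.

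This is a worthwhile correction to the safety tables, not a flaw that invalidates the analysis.

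**What to change.** In Section 11.4.2.2:

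- Keep the by-timepoint laboratory counts, with the Day 1 count beside each later one.
- Add, by cohort, laboratory shift tables of baseline CTCAE v5 grade against worst post-dose grade, with number and percentage worsening by at least one and at least two grades.
- Define baseline as the last value before the first on-study dose. This matters in the two-dose cohorts, where the Day 29 sample follows dose 1 and precedes dose 2.
- For vaccine-naïve participants moving to a booster, use the last available pre-booster value or report them as having no booster-specific baseline, because Section 6.1.3 does not require baseline labs for them.
- For vital signs, add change from baseline and replace the reference to laboratory ranges with Appendix D grades, pre-dose against post-dose, with a caution on one-grade shifts.
- Remove coagulation.

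The cost is SAP wording and routine programming, largely on data already collected. There are three limits. Participants at the worst grade at baseline cannot show a shift. Some booster participants will lack a baseline. Worst post-dose grade depends on how many samples each participant has, and booster Day 8 is mandatory only for the CAR T cohort.
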